6.2.3 Duration of Best Response

The duration of overall response is measured from the time measurement criteria are met for best response until the first date that recurrent or progressive disease is objectively documented.

6.2.4 Progression-Free Survival

PFS is defined as time of start of treatment to time of progression or death, whichever occurs first.

6.2.5 Overall Survival

Overall survival is defined as the time of start of treatment to death from any cause.

6.2.6 Overall response rates

Overall response rates (ORR) is PR+VGPR+CR after n cycles of therapy.

6.3 TOXICITY CRITERIA

The following adverse event management guidelines are intended to ensure the safety of each patient while on the study. The descriptions and grading scales found in the revised NCI Common Terminology Criteria for Adverse Events (CTCAE) version 4.0 will be utilized for AE reporting. All appropriate treatment areas should have access to a copy of the CTCAE version 4.0. A copy of the CTCAE version 4.0 can be downloaded from the CTEP web site (http://ctep.cancer.gov/protocolDevelopment/electronic_applications/ctc.htm#ctc_40).

Attribution of the AE:

- Definite: The AE is clearly related to the study treatment.
- Probable: The AE is likely related to the study treatment.
- Possible: The AE may be related to the study treatment.
- Unlikely: The AE is doubtfully related to the study treatment.
- Unrelated: The AE is clearly NOT related to the study treatment.

7 SAFETY REPORTING REQUIREMENTS/DATA AND SAFETY MONITORING PLAN

7.1 DEFINITIONS

7.1.1 Adverse Event

An adverse event is defined as any reaction, side effect, or untoward event that occurs during the course of the clinical trial associated with the use of a drug in humans, whether or not the event is considered related to the treatment or clinically significant. For this study, AEs will include events reported by the patient, as well as clinically significant abnormal findings on physical examination or laboratory evaluation. A new illness, symptom, sign or clinically significant laboratory abnormality or worsening of a pre-existing condition or abnormality is considered an AE. All AEs that are Grade 3 or higher must be recorded on the AE case report form.

All AEs, including clinically significant abnormal findings on laboratory evaluations, regardless of severity, will be followed until return to baseline or stabilization of event. Serious adverse events that occur more than 30 days after the last administration of investigational agent/intervention and have an attribution of at least possibly related to the agent/intervention should be recorded and reported as per section **7.2**.

An abnormal laboratory value will be considered an AE if the laboratory abnormality is characterized by any of the following:

- Results in discontinuation from the study
- Is associated with clinical signs or symptoms
- Requires treatment or any other therapeutic intervention
- Is associated with death or another serious adverse event, including hospitalization.
- Is judged by the Investigator to be of significant clinical impact
- If any abnormal laboratory result is considered clinically significant, the investigator will provide details about the action taken with respect to the test drug and about the patient's outcome.

7.1.2 Suspected adverse reaction

Suspected adverse reaction means any adverse event for which there is a reasonable possibility that the drug caused the adverse event. For the purposes of IND safety reporting, 'reasonable possibility' means there is evidence to suggest a causal relationship between the drug and the adverse event. A suspected adverse reaction implies a lesser degree of certainty about causality than adverse reaction, which means any adverse event caused by a drug.

7.1.3 Unexpected adverse reaction

An adverse event or suspected adverse reaction is considered "unexpected" if it is not listed in the investigator brochure or is not listed at the specificity or severity that has been observed; or,

if an investigator brochure is not required or available, is not consistent with the risk information described in the general investigational plan or elsewhere in the current application.

"Unexpected", also refers to adverse events or suspected adverse reactions that are mentioned in the investigator brochure as occurring with a class of drugs or as anticipated from the pharmacological properties of the drug, but are not specifically mentioned as occurring with the particular drug under investigation.

7.1.4 Serious

An Unanticipated Problem or Protocol Deviation is serious if it meets the definition of a Serious Adverse Event or if it compromises the safety, welfare or rights of subjects or others.

7.1.5 Serious Adverse Event

An adverse event or suspected adverse reaction is considered serious if in the view of the investigator or the sponsor, it results in any of the following:

- Death,
- A life-threatening adverse drug experience
- Inpatient hospitalization or prolongation of existing hospitalization
- Persistent or significant incapacity or substantial disruption of the ability to conduct normal life functions
- A congenital anomaly/birth defect.
- Important medical events that may not result in death, be life-threatening, or require hospitalization may be considered a serious adverse drug experience when, based upon appropriate medical judgment, they may jeopardize the patient or subject and may require medical or surgical intervention to prevent one of the outcomes listed in this definition.
Per Celgene: Examples of such events include allergic bronchospasm requiring intensive treatment in an emergency room or at home, blood dyscrasias or convulsions that do not result in inpatient hospitalization, or the development of drug dependency or drug abuse. A new diagnosis of cancer during the course of a treatment should be considered as medically important.
- Pregnancy

7.1.6 Disability

A substantial disruption of a person's ability to conduct normal life functions.

7.1.7 Life-threatening adverse drug experience

Any adverse event or suspected adverse reaction that places the patient or subject, in the view of the investigator or sponsor, at immediate risk of death from the reaction as it occurred, i.e., it does not include a reaction that had it occurred in a more severe form, might have caused death.

7.1.8 Protocol Deviation (NIH Definition)

Any change, divergence, or departure from the IRB approved research protocol.

Abbreviated Title: Revlimid maintenance for MM

Version Date: 01/06/2017

7.1.9 Non-compliance (NIH Definition)

The failure to comply with applicable NIH Human Research Protections Program (HRPP) policies, IRB requirements, or regulatory requirements for the protection of human research subjects.

7.1.10 Unanticipated Problem

Any incident, experience, or outcome that:

- Is unexpected in terms of nature, severity, or frequency in relation to
 - (a) the research risks that are described in the IRB-approved research protocol and informed consent document; Investigator's Brochure or other study documents, and
 - (b) the characteristics of the subject population being studied; **AND**
- Is related or possibly related to participation in the research; **AND**
- Suggests that research places subjects or others at a *greater risk of harm* (including physical, psychological, economic, or social harm) than was previously known or recognized.

7.1.11 Pregnancies

7.1.11.1 Reporting Pregnancy to Celgene

Pregnancies and suspected pregnancies (including a positive pregnancy test regardless of age or disease state) of a female subject occurring while the subject is on lenalidomide, or within 28 days of the subject's last dose of lenalidomide, are considered immediately reportable events. Lenalidomide is to be discontinued immediately. The pregnancy, suspected pregnancy, or positive pregnancy test must be reported to Celgene Drug Safety immediately by facsimile or email using the Pregnancy Initial Report Form. The female subject should be referred to an obstetrician-gynecologist, preferably one experienced in reproductive toxicity for further evaluation and counseling.

The Investigator will follow the female subject until completion of the pregnancy, and must notify Celgene Drug Safety immediately about the outcome of the pregnancy (either normal or abnormal outcome) using the Pregnancy Follow-up Report Form. If the outcome of the pregnancy was abnormal (e.g., spontaneous or therapeutic abortion), the Investigator should report the abnormal outcome as an AE. If the abnormal outcome meets any of the serious criteria, it must be reported as an SAE to Celgene Drug Safety immediately by facsimile, or other appropriate method, within 24 hours of the Investigator's knowledge of the event using the SAE Report Form.

All neonatal deaths that occur within 28 days of birth should be reported, without regard to causality, as SAEs. In addition, any infant death after 28 days that the Investigator suspects is related to the in utero exposure to the investigational product (IP) should also be reported to Celgene Drug Safety immediately by facsimile, or other appropriate method, within 24 hours of the Investigator's knowledge of the event using the SAE Report Form.

Male Subjects

Abbreviated Title: Revlimid maintenance for MM

Version Date: 01/06/2017

If a female partner of a male subject taking investigational product becomes pregnant, the male subject taking lenalidomide should notify the Investigator, and the pregnant female partner should be advised to call her healthcare provider immediately.

Celgene Drug Safety Contact Information:

Celgene Corporation
Global Drug Safety and Risk Management
[name]
[name]
[name]
[contact]
E-mail: [contact]

7.2 NCI-IRB REPORTING

7.2.1 NCI-IRB Expedited Reporting of Unanticipated Problems and Deaths

The Protocol PI will report to the NCI-IRB:

- All deaths, except deaths due to progressive disease
- All Protocol Deviations
- All Unanticipated Problems
- All serious non-compliance

Reports must be received by the NCI-IRB within 7 working days of PI awareness via iRIS.

7.2.2 NCI-IRB Requirements for PI Reporting at Continuing Review

The protocol PI will report to the NCI-IRB:

1. A summary of all protocol deviations in a tabular format to include the date the deviation occurred, a brief description of the deviation and any corrective action.
2. A summary of any instances of non-compliance
3. A tabular summary of the following adverse events:
 - All Grade 3 and 4 events that are possibly, probably or definitely related to the research;
 - All Grade 5 events regardless of attribution;
 - All Serious Events regardless of attribution.

NOTE: Grade 1 and Grade 2 events are not required to be reported.

7.2.3 NCI-IRB Reporting of IND Safety Reports

Only IND Safety Reports that meet the definition of an unanticipated problem will need to be reported to the NCI IRB.

Abbreviated Title: Revlimid maintenance for MM

Version Date: 01/06/2017

7.2.4 SAE Reporting to Celgene

All adverse experience reports must include the patient number, age, sex, weight, severity of reaction (e.g. mild, moderate, severe), relationship to drug (e.g. probably related, unknown relationship, definitely not related), date and time of administration of test medications and all concomitant medications, and medical treatment provided. The investigator is responsible for evaluating all adverse events to determine whether criteria for “serious” and as defined above are present. The investigator is responsible for reporting adverse events to Celgene as described below.

Serious adverse events (SAE) are defined above. The investigator must inform Celgene in writing using a Celgene SAE form or MEDWATCH 3500A form of any SAE as soon as possible or at least within 24 hours of being aware of the event. The date of awareness should be noted on the report. The written report must be completed and supplied to Celgene by facsimile within 24 hours/1 business day at the latest on the following working day. The initial report must be as complete as possible, including an assessment of the causal relationship between the event and the investigational product(s), if available. Information not available at the time of the initial report (e.g., an end date for the adverse event or laboratory values received after the report) must be documented on a follow-up report. A final report to document resolution of the SAE is required. The Celgene tracking number (RV-MM-NCI-0718) and the institutional protocol number should be included on SAE reports (or on the fax cover letter) sent to Celgene. A copy of the fax transmission confirmation of the SAE report to Celgene should be attached to the SAE and retained with the patient records.

Celgene Corporation
Drug Safety
[name]
[name]
Toll Free: [contact]
[contact]
[contact]
E-mail: [contact]

7.3 DATA AND SAFETY MONITORING PLAN

The following plans will be used for this study.

7.3.1 Principal Investigator/Research Team

The clinical research team will meet on a regular basis when patients are being actively treated on the trial to discuss each patient in detail. Decisions about dose level enrollment and dose escalation if applicable will be made based on the toxicity data from prior patients.

All data will be collected in a timely manner and reviewed by the principal investigator or a lead associate investigator in a timely manner. Adverse events will be reported as required above. Any safety concerns, new information that might affect either the ethical and or scientific conduct of the trial, or protocol deviations will be immediately reported to the IRB using iRIS and if applicable to the Sponsor.

Abbreviated Title: Revlimid maintenance for MM

Version Date: 01/06/2017

The principal investigator will review adverse event and response data on each patient to ensure safety and data accuracy. The principal investigator will personally conduct or supervise the investigation and provide appropriate delegation of responsibilities to other members of the research staff.

8 STATISTICAL CONSIDERATIONS

8.1 STUDY DESIGN/PRIMARY ENDPOINTS

This is a single arm, single stage, phase II trial to evaluate maintenance therapy with the immunomodulatory agent lenalidomide in treated MM patients who have stable or responsive disease. After screening, eligibility determination, and enrollment; subjects will receive lenalidomide 10 mg by mouth daily on days 1-21 of a 28-day cycle. Subjects may continue lenalidomide until disease progression, diagnosis of new malignancy, unacceptable toxicity, investigator discretion, or voluntary withdrawal. When necessary, lenalidomide will be held and restarted in accordance with accepted clinical dose modification strategies.

The primary objective of this study is a longitudinal assessment of T cell (CD4, CD8), NKT and NK cell populations during the course of lenalidomide maintenance therapy in patients with MM. Using flow cytometry on peripheral blood obtained at baselines and after 3 cycles of therapy, we will determine the primary measures at both time points. Comparisons at other time points will be considered exploratory..

With 28 patients enrolled, we will have 80% power to detect an effect equal to 0.67 SD of the difference in counts (0.67 SD effect size) of T cells (CD4, CD8), NKT and NK cells with a two-tailed paired t-test and a significance level of 0.013 for each test. Thus, using a strict Bonferroni adjustment, we would have an overall significance level of 0.05 for the four tests. In practice, a less overly conservative Hochberg adjustment may be used instead of a Bonferroni adjustment. In addition, if the difference in the numbers of any type of cells is not normally distributed ($p < 0.05$ by a Shapiro- Wilks test), then a Wilcoxon signed rank test will be performed instead.

Results will be presented in a descriptive format.

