3 STUDY IMPLEMENTATION

3.1 STUDY DESIGN

- Patients with newly diagnosed or relapsed MM with stable disease or better clinical response after induction or re-induction treatment will be enrolled on this phase II study and treated with a maintenance dose of lenalidomide 10 mg daily on days 1 to 21 of repeated 28-day cycles.
- Patients who complete at least 3 cycles will be evaluable for primary endpoints. Patients who do not complete three cycles of therapy will not be included in the analysis of primary or non-primary endpoints; and will be replaced by new patients.
- Using flow cytometry on peripheral blood, the four primary outcomes of T cell (CD4, CD8), NKT and NK cell numbers will be measured at pre-specified treatment time points to determine the difference in the counts of these parameters for each patient.

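### The per-test level of 0.013 is slightly above the strict Bonferroni level of 0.0125, and the final multiplicity procedure for the four primary tests is left open

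*Combined protocol and SAP*

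**What the plan says.** Section 3.1 names "the four primary outcomes of T cell (CD4, CD8), NKT and NK cell numbers". Section 8.1 compares each of them between two visits ("Using flow cytometry on peripheral blood obtained at baselines and after 3 cycles of therapy") and adds that "Comparisons at other time points will be considered exploratory". The confirmatory family is therefore four tests, one per cell type.

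The sizing statement in 8.1 reads "With 28 patients enrolled, we will have 80% power" for an effect of 0.67 SD of the paired difference, "with a two-tailed paired t-test" and "a significance level of 0.013 for each test". The next sentence says that, "using a strict Bonferroni adjustment, we would have an overall significance level of 0.05 for the four tests". The section then adds that in practice "a less overly conservative Hochberg adjustment may be used instead of a Bonferroni adjustment". It does not say when that choice is made or on what basis. The value 0.0125 does not appear, and 0.013 is not described as rounded.

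**The concern.** There are two linked points. First, 0.013 is the only per-test level in the document, and it does not deliver the overall level that the plan attaches to it under strict Bonferroni. If an analyst applied it literally, a p-value between 0.0125 and 0.013 would be declared significant although strict Bonferroni at 0.05 would not allow it.

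Second, Bonferroni and Hochberg can declare different sets of endpoints significant from the same data, and the plan does not say which one governs. If the choice is made after the p-values are known, a reader cannot tell which rule was prespecified.

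**Working it through.** **Inputs (all from 8.1 unless noted).** Four tests (also 3.1); per-test level 0.013; overall level 0.05; n = 28; effect d = 0.67 SD of the difference; two-sided paired t-test. Section 3.1 replaces patients who do not complete three cycles, so 28 is taken as the number of complete pairs.

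**1. The plan's power figure.** Degrees of freedom are 27 and the noncentrality is 0.67 x sqrt(28) = 3.545. The exact noncentral-t power at two-sided 0.013 is 80.4%. The stated 80% is reproduced, and 28 is the smallest n that reaches it at that level.

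**2. The overall level.**

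| Per-test level | Bonferroni bound (4 x level) | Family-wise error if independent, 1 - (1 - level)^4 |
|---|---|---|
| 0.013 | 0.052 | 0.0510 |
| 0.0125 | 0.0500 | 0.0491 |

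The Šidák level, 1 - 0.95^(1/4) = 0.01274, is also below 0.013, so assuming independence does not recover 0.05. The documents give no correlations between the four changes. With assumed common correlations, simulated family-wise error at 0.013 (n = 28, normal differences) was 4.7% to 4.9% at correlation 0.3 across repeated simulations, and 4.2% at 0.6.

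**3. Power at the corrected level.** At 0.0125 with n = 28 and d = 0.67, power is 79.97%. The effect detectable with exactly 80% power is 0.6702 SD, against 0.6670 SD at 0.013. Both round to 0.67. Read to the last decimal, 79.97% is just short of 80% and n = 29 would give 81.8%, but at the plan's own precision 28 patients, 0.67 SD and 80% all stand.

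**4. Hochberg or Holm against Bonferroni at 0.0125.** With ordered p-values p(1) to p(4), both procedures at 0.05 compare p(j) with 0.05/(4 - j + 1), that is 0.0125, 0.0167, 0.025 and 0.05. Any p-value at or below 0.0125 lies under its own threshold, and so do all smaller ones, so both procedures reject it. Neither can lose a rejection that Bonferroni at 0.0125 makes.

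This does not hold against a literal 0.013. A lone p of 0.0128, with the other three above 0.05, passes 0.013 but fails Hochberg and Holm.

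**5. Size of the Hochberg gain.** These are simulations with n = 28, real effects of 0.67 SD, the remaining effects zero, and assumed correlations of 0 to 0.6. Average power per real endpoint under Bonferroni at 0.0125 is about 80%.

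| Real effects among the four | Gain with Hochberg at 0.05 |
|---|---|
| One | about 0.2 points |
| Two | about 3 points |
| All four | about 10 to 11 points |

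When all four are real, Bonferroni at 0.013 and Hochberg at 0.05 gave different sets of significant endpoints in 37%, 32% and 27% of simulated trials at correlations 0, 0.3 and 0.6.

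**The case against.** The strongest reply is that this is rounding: 0.0125 to three decimals is 0.013, and 0.052 to two decimals is 0.05. The figure 0.013 stands in the sizing sentence, and Hochberg run at an overall 0.05 would never use it. Section 8.1 also says that results will be presented descriptively, and this is a 28-patient single-arm biomarker study. Most of this stands, and it is why the error is small. It does not remove the point, because the section calls the adjustment strict, gives no other per-test level, and specifies formal tests with family-wise control.

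Three stronger readings are tempting, and the documents do not support them:

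- A reader might infer that the sample size or power is wrong. It is not: power is 79.97% at the corrected level.
- A reader might infer that the true family-wise error exceeds 5%. The 0.052 is a bound. The error is 5.1% under independence and falls below 5% with moderate positive correlation.
- A reader might infer that 0.013 is the fixed decision threshold for all four tests. The text uses it for sizing and leaves the final procedure open.

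It is also fair to object that a 10 to 11 point Hochberg gain is the best case. The plan does not claim that all four effects are 0.67 SD, so the gain has to be given as a range.

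**Conclusion.** The point holds as a small threshold error together with an incomplete prespecification. The stated 0.013 guarantees an overall 0.052 where the plan claims 0.05, an excess of 0.2 percentage points on the bound and 0.1 under independence.

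The open choice of procedure matters more than the digit. Its effect ranges from almost nothing with one real effect to a different set of significant endpoints in roughly a third of trials when all four effects are 0.67 SD. The bound and the power figures follow from the plan's own numbers, with 28 complete pairs. The family-wise error under correlation and the Hochberg gains rest on assumed correlations, normal differences and the assumed number of real effects.

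**What to change.** In 8.1, write the sizing level as 0.0125 (0.05/4) and keep 28 patients, 0.67 SD and 80% power. Replace the optional wording on Hochberg with a commitment made before the primary data are analysed: Bonferroni for sizing only, and one named procedure at family-wise 0.05 for the four primary p-values.

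Hochberg is the plan's own suggestion and is at least as powerful as Holm. Holm needs no assumption about dependence between the four cell types, which may be preferred because the documents give no correlations. The same procedure should take the p-value from the Wilcoxon signed rank test wherever 8.1 substitutes it for the t-test.

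The cost is one number and one sentence, with no change to sample size, visits or assays.
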